15.1 Assessment of Safety Event Report Forms

Safety reports will be assessed based on the seriousness, causality, and expectedness of the event to the trial treatment(s), intervention(s), investigational medical product(s), investigational medical device(s). The following are known and expected adverse effects, harms, risks, or discomforts associated with trial procedures, treatments or interventions.

a) Known Adverse Effects

- minor side-effects of medications used in this study (e.g., corneal abrasions, eye irritation, eye pain, blurred vision and/or problems seeing clearly, photophobia),
- the discomforts related to optometric measurements (e.g., tearing, potential corneal abrasions)
- the discomfort related to the skin prick test (e.g., swelling of the examined area, feeling of dizziness, light-headedness)

b) Known Harms, Risks or Discomforts

- Ocular medication harms: including injury, punctate keratitis, severe corneal erosion, severe corneal abrasions, and cataract.

15.2 Adverse Events or Adverse Reactions

Adverse events (AE) are defined as any untoward medical occurrence in a patient or clinical trial participant administered the investigational medical product or intervention, which does not necessarily have a causal relationship with this treatment.

Adverse Reactions (AR) are defined as any untoward and unintended response to the trial intervention related to any dose administered.

AEs and ARs are assessed using the safety monitoring flow chart. Those classified as "not serious" are assessed by the qualified physician/medical expert specified in section 2 of the protocol. The Qualified Physician cannot delegate this responsibility to other research personnel.

Adverse event will be monitored and reported annually to HREC. In addition, all adverse event reports must be recorded in the [UNSW Safety Monitoring Register Template](#).

15.3 Serious Adverse Events

Serious Adverse Events (SAEs) that result in or lead to one or more of the following and the event is **not related** to the investigational medical product, the trial intervention, or procedures:

- The death of a trial participant.
- A life-threatening illness or injury involving a trial participant.
- A participant's permanent impairment of body structure or body function.
- A trial participant is an in-patient or prolonged hospitalisation (not for a pre-existing condition or an elective surgery).
- Medical or surgical intervention to prevent life-threatening illness or injury or permanent impairment to a body structure or function of a trial participant.
- Fetal distress, fetal death, congenital abnormality or birth defect.

SAE reports are classified following the safety assessment flowchart and are assessed by Sponsors Independent Medical specified in section 2 of the protocol. The Sponsors Independent Medical cannot delegate this responsibility to other research personnel. SAE reports are reported to HREC within 48 hours. SAR reports must be recorded in the [UNSW Safety Monitoring Register Template](#).

15.4 Serious Adverse Reactions

A Serious Adverse Reactions (SAR) is an SAE **related** to the investigational medical product, the trial intervention, or procedures. SAR reports are classified following the safety assessment flowchart and are assessed by Sponsors Independent Medical specified in section 2 of the protocol. The sponsors independent medical expert must determine whether the SAR was expected or unexpected. The Sponsors Independent Medical cannot delegate this responsibility to other research personnel.

a) Expected Serious Adverse Reaction

A serious adverse reaction by its nature, incidence, severity, or outcome is anticipated and identified in the current investigational medical product or intervention safety information, classified as a SAR report. SAR reports are reported to the Coordinating Principal Investigator 48 hours. In addition, serious Adverse Reaction reports must be recorded in the [UNSW Safety Monitoring Register Template](#).

b) Suspected Unexpected Serious Adverse Reaction (SUSAR)

A serious adverse reaction by its nature, incidence, severity, or outcome is unanticipated and not identified in the investigational medical product, the trial intervention, or procedures for use safety information are classified as a SUSAR.

Fatal or life-threatening Australian SUSAR reports are reported to the Therapeutic Goods Administration, the Coordinating Principal Investigator, and the sponsor's delegate within seven calendar days after being made aware of the case follow up information reported within a further eight calendar days.

All other Australian SUSAR reports are to be reported to the Therapeutic Goods Administration, the Coordinating Principal Investigator, and the sponsor's delegate within 15 calendar days after being made aware of the case follow up information reported within a further eight calendar days. In addition, SUSAR reports must be recorded in the [UNSW Safety Monitoring Register Template](#).

15.5 Significant Safety Issue (SSI)

A safety issue that could adversely affect participants' safety or materially impact the trial's continued ethical acceptability or conduct. The Therapeutic Goods Administration, Human Research Ethics Committee and Sponsor's Delegate must notify all significant safety issues within 15 calendar days of the sponsor instigating or being made aware of the issue. SSI reports must be recorded in the [UNSW Safety Monitoring Register Template](#).

[figure not shown]
15.6 Urgent Safety Measure (USM)

A measure that is taken to eliminate an immediate hazard to a participant's health or safety. Significant safety issues requiring an urgent safety measure to be taken to eliminate an immediate hazard must be classified as a significant safety issue requiring an urgent safety measure. The Therapeutic Goods Administration, Human Research Ethics Committee and the Sponsor's Delegate must be notified of any significant safety issues that meet the definition of an urgent safety measure should be notified within 72 hours. Examples include:

- a serious adverse event that could be associated with the trial procedures and that requires modification of the conduct of the trial.
- A patient population hazard, such as lack of efficacy of intervention used to treat a life-threatening disease.

USM reports must be recorded in the [UNSW Safety Monitoring Register Template](#).

15.7 Safety Assessment Flow Chart Investigational Medical Product Trials

15.8 Register of Clinical Trial Safety Monitoring Reports

A register of all event reports assessed and classified is to be retained by the Coordinating Principal Investigator and reported to the trial sponsor annually and the HREC if required.

15.9 Reporting of Clinical Trial Safety Monitoring Reports

Single case reports of Adverse Events Adverse Reactions, Serious Adverse Events (SAEs), and Serious Adverse Reactions (SARs) do not need to be reported to the UNSW Sponsor's Delegate or the HREC. However, all case reports must be recorded in a safety monitoring register and reported annually to the UNSW Sponsor's Delegate.

a) Emerging Safety Issues

The [Trial Management Group](#), [Trial Safety Committee](#) is responsible for reviewing the safety information to identify any serious emerging safety concerns. If safety concerns are identified, this body will establish a plan to minimise the time participants may be placed at

excess risk of harm. Before implementing the plan, the [Trial Management Group](#), [Trial Safety Committee](#) must seek the advice of the human research ethics committee.

b) Annual assessment of safety

The following information must be provided in a report annually:

- Documented evidence that the [Trial Management Group](#), [Trial Safety Committee](#), or the [Data Safety Monitoring Board](#) (e.g., meeting minutes) confirmed that regular safety reviews occurred.
- Analysis of the trial intervention(s) and its implications for participants considering all available safety data and relevant clinical or non-clinical studies results.
- Any reports of emerging safety issues and a description of any measures taken or proposed to minimise risks.
- A copy of the safety monitoring register.

16. Non-compliance, Protocol Deviation and Serious Breaches of Good Clinical Practice

16.1 Protocol Deviation

A protocol deviation is defined as any breach, divergence or departure from the requirements of Good Clinical Practice, the clinical trial protocol, the clinical trial standard operating procedures, or the human ethics approval that does not have a significant impact on the continued safety or rights of participants or the reliability and robustness of the data generated in the research or clinical trial. Protocol deviations are events that do not occur persistently or systematically and do not potentially result in participant harm. Examples of protocol deviations include but are not limited to:

- Deviations because of participant adherence to the protocol, including rescheduled study visits, participants refusal to complete scheduled research activities or failure to complete self-report questionnaires required by the study protocol.
- Blood samples obtained or clinical trial testing occurring at times close to, but not precisely at the time specified in the protocol.
- The completion of consent forms, safety monitoring reports, case report forms or data collection tools in a manner that is not consistent with the protocol instructions or failure to make reports within the required reporting timeframes.
- Administration of the clinical trial investigational medical product or device in a manner that is not consistent with the manufacturer's instructions for use.
- Use an unapproved version of the participant information statement or recruitment of participants using unapproved recruitment procedures.
- Inclusion of a participant that does not meet the inclusion criteria.
- An urgent safety measure must be taken to eliminate an immediate hazard to a participant's health or safety.

16.2 Serious Breach of Good Clinical Practice

A serious breach is defined as a breach of Good Clinical Practice, the clinical trial protocol, the clinical trial standard operating procedures, or the human ethics approval that is likely to affect to a significant degree the safety or rights of participants or the reliability and robustness of the data generated in the clinical trial. Examples of serious breaches include but are not limited to:

- Persistent or systematic non-compliance with the instructions for completing consent forms, safety monitoring forms, case report forms or data collection tools result in continued missed or incomplete data collection.

- Failure to record or report adverse events, serious adverse events, suspected unexpected serious adverse reactions, significant safety issues where urgent safety measures were implemented.
- Failure to conduct clinical trial procedures following the clinical trial delegation log.
- Widespread and uncontrolled use of protocol waivers or deviations from eligibility criteria that (or has the potential to) harm trial subjects.
- Failure to report investigational medical product or device defects to the clinical trial sponsor or any relevant regulatory body.
- Failure to conduct research following the issued approvals, permits or licences by required laws, regulations, disciplinary standards, and UNSW policies relating to research's responsible or safe conduct.
- Concealing or facilitating breaches (or potential breaches) of the Research Code by others.
- Researching without the requisite approvals, permits or licences required by laws, regulations, disciplinary standards, and UNSW policies related to research's responsible or safe conduct.
- Failure to conduct research as approved by an ethics review body where that conduct leads to (or has the potential to) results in participant harm.
- Researching without ethics approval as required by the National Statement on Ethical Conduct in Human Research where that conduct leads to (or has the potential to) result in participant harms.
- Any breaches as outlined in the UNSW Research Misconduct Procedure or the Australian Code for responsible conduct of research that leads to (or has the potential to) result in participant harm.

16.3 Reporting Protocol Deviations

- Protocol deviations occurring at a site must be documented in site files and reported to the Coordinating Principal Investigator by the principal site investigator.
- The Coordinating Principal Investigator must review the protocol deviation and the clinical trial protocol to establish the corrective actions and preventative steps to prevent the deviation from reoccurring.
- The protocol deviation and corrective action plan must be reported to the UNSW Sponsor's Delegate by the Coordinating Principal Investigator or Coordinating Research Team.

16.4 Reporting of a Serious Breach

- A serious breach occurring at a participating site must be reported by the site Principal Investigator to the Coordinating Principal Investigator within a specified timeframe.
- The Coordinating Principal Investigator must review the serious breach, along with the clinical trial protocol, to develop a Corrective and Preventive Action (CAPA) that defines the steps to prevent the serious breach from reoccurring.
- The serious breach report and the CAPA must be provided to the approving HREC, and the UNSW sponsors delegate for review and approval.

16.5 Reporting of Serious Breaches by Third Parties

- A Suspected Breach is a report judged by the reporter as a possible serious breach but has yet to be formally confirmed as a serious breach by the sponsor.
- A Suspected Breach form must be completed when a third party (e.g., individual/institution) wishes to report a suspected breach of Good Clinical Practice or the protocol and should be reported directly to the reviewing HREC.
- Recording of Protocol Deviation and Serious Breach Reports
- A register of protocol deviation and serious breach reports must be recorded. In addition, written records and copies of documentation must be retained in the Investigator Site File.

- Copies of protocol deviation and serious breach reports must be recorded, written records and copies of documentation, referrals made to the HREC or establishing whether a breach of the Australian Code for Responsible conduct of research must be retained in the Master Site File.

17. Review of a Protocol Deviation and a Serious Breach

- The UNSW Sponsor's Delegate will review reports to establish whether the event meets the definition of a protocol deviation or serious breach, establish whether the proposed CAPA is appropriate and establish whether there is or will be an ongoing impact on the reliability and robustness of the data generated.
- The UNSW Sponsor's Delegate will seek advice from the approving HREC on the corrective and preventive actions.
- Protocol deviation or serious breach reports where a UNSW researcher, staff or student is responsible for the protocol deviation or the serious breach will be reviewed as per the UNSW Research Misconduct Procedure to establish whether a breach of the UNSW Research Code Conduct has occurred.
- Protocol deviation or serious breach reports where the UNSW Sponsor's Delegate determines that site personnel are responsible for a protocol deviation or the serious breach will be referred onto their responsible institution for review under their Research Misconduct procedures to establish whether a breach of the Australian Research Code for the Responsible Conduct of Research has occurred.

18. Statistics

- SPSS software (version 28.0; SPSS inc.) will be used. Differences in symptoms and signs between treatment groups and the control group will be assessed using the Independent Sample t-test or Mann-Whitney U test, as appropriate. For dendritic cell density, A linear mixed model with effect for individuals will be used to examine differences in (log) dendritic cell density between groups and between corneal and conjunctival locations. Pairwise comparisons between groups and locations will be obtained within the model. P-values for multiple comparisons between locations will be adjusted by Holm's step-down Bonferroni method.
- Mann-Whitney U test (for cell body size) and Fisher's Exact test (for the presence of dendrites) will be used to assess differences in dendritic cell morphology between groups. Friedman, and Wilcoxon Signed Ranked Test (for cell body size) and Cochran's Q Test (for the presence of dendrites) will be used to assess differences in dendritic cell morphology across locations and the p-values for pairwise comparison between locations were adjusted by Holm's step-down Bonferroni method.
- Associations between dendritic cell and ocular surface symptoms and signs will be assessed using a univariate Spearman's correlation coefficient (for dendritic cell density and cell body size) and Mann-Whitney U test (for the presence of dendrites).

19. Data Handling, Ownership and Access

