In a recently published article, dendritic cell density was higher in participants with allergic conjunctivitis at the corneal centre, corneal periphery, limbus, and conjunctiva but not at the inferior whorl, compared to controls [21]. Dendritic cell density was highest at the limbus followed by the corneal periphery and the lowest density was at the conjunctiva, and there was no difference between the corneal centre and the inferior whorl [21]. Dendritic cell morphology assessment was based on cell body size (small, medium, large), and the presence of any dendrites, the presence of long dendrites, and the presence of thick dendrites [21]. At corneal centre, dendritic cell had a larger cell body size, and there was a higher percentage of dendritic

cell with dendrites and with long dendrites in the allergic conjunctivitis group [21]. Cell body size, the presence of long dendrites and the presence of thick dendrites were not significantly different between groups at other locations [21]. When allergic participants were symptom free, corneal dendritic cell body size was smaller and there were fewer dendritic cell with long dendrites [22]. At the bulbar conjunctiva, dendritic cell density was reduced during the symptom-free phase but did not change in morphology [22].

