The Perkins tonometer is a handheld applanation model used to measure intraocular pressure. The principle of applanation tonometry is based on the force required to flatten a certain area of the spherical surface of the cornea is the same as the pressure inside the eye. The Perkins tonometer is a very popular handheld applanation tonometer used in humans.

- **The Oculus Keratograph 5M (K5)**

This is an advanced corneal topographer with a built-in real keratometer and a colour camera optimized for external imaging. In our study the tear film break-up time will be measured automatically and non-invasively.

- **Slit lamp biomicroscopy**

The ocular surface and anterior segment will be examined using a slit lamp biomicroscope and ocular surface signs, including conjunctival and limbal redness (graded using the Cornea and Contact Lens Research Unit (CCLRU) grading scale), conjunctival chemosis, papillae and follicles (graded using the Japanese grading scale for allergic conjunctivitis [8]).

- **Ocular staining**

A wetted fluorescein strip (harmless yellow dye) and a wetted lissamine green strip (harmless green dye) will be then gently touched to the fornix of the lower lid. Participants will be asked to blink continuously to enable the smooth spreading of the stain over the eye, allowing for the evaluation of any surface defects. Ocular surface (corneal and conjunctival) staining will be assessed using the Oxford grading scale [9]. These dyes are routinely used in optometry practices worldwide and are safe to use.

- **Confocal microscopy**

A confocal microscope will be used to visualise the corneal sub-basal corneal nerves and dendritic cell in vivo. A probe that emits harmless laser light will come in contact with the transparent front part of the eye for approximately 5 minutes, and microscopic images of the cornea will be captured. Images will be captured from the right eye only. To avoid any discomfort to the patient or causing abrasions on the transparent surface of the eye a topical anaesthetic will be installed in the tested eye and a soft lubricating gel will be applied over the microscope probe.

All the above-mentioned clinical procedures (except the Skin Prick Test) will be repeated for the eligible participants at the follow-up visits.

Reference list

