After taking history, participants will be asked to complete questionnaires (eligibility phase 1), related to eye and nose allergy symptoms: Numerical Rating Scale (NRS), Mini Rhinoconjunctivitis Quality of Life Questionnaire (Mini-RQLQ), Ocular Surface Disease Index (OSDI), Aston University Allergy Questionnaire (AUAQ), the dry eye questionnaire for the detection of dry eye (Dry Eye Questionnaire: DEQ-5) and the Eye Allergy Patient Impact Questionnaire (EAPIQ). Changes in symptoms during the treatment will be recorded using a Numerical Rating Scale (NRS). Changes in symptoms and signs will be recorded, reported and analysed from both eyes as appropriate. Each questionnaire includes detailed instructions on how to complete them. To confirm participants' allergy status, a Skin Prick Test will be conducted (eligibility phase 2) where a drop of allergen will be placed on the forearm, and a slight skin prick will be made using a lancet at the same spot to allow the allergen to be absorbed by the skin. Ten minutes later, the skin's allergic reaction will be determined by measuring the size of the hive formed on the skin. Visual acuity, Tearscope and ocular surface health integrity with white light slit lamp biomicroscopy will follow. Ocular staining will be performed before and after each time taking confocal microscopy images.

Ocular surface dendritic cell images will be taken using the *in vivo* confocal microscopy (IVCM) at the baseline visits and at each follow-up visit. A topical anaesthetic eyedrops will be applied to the examined eye of the participants (right eye) and a soft lubricating gel will be applied over the microscope probe to avoid any discomfort. Participants will be directed to look at a single white fixation light with the contralateral eye to help maintain head posture and eye position. A gentle touch by the IVCM probe will be apply on the corneal surface (the transparent front part of the eye) to capture multiple images from different locations on the cornea.

After the baseline visit, participants will be randomly given either treatment or control eyedrops and instructed to put one drop in each eye, twice daily for two weeks. Participants will be asked to visit the clinic at different interval periods including 24 hours, 7 days and 14 days during the treatment period, and post-treatment at days 21 and 28, to repeat all the examinations except the Skin Prick Test (Table 1).

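### The density model names individuals as its only dependence term; fitted to all six visits together, it can give location p-values that are too small and mis-size some arm contrasts

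*Protocol*

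**What the plan says.** Section 18 (Statistics) gives one model for density: "A linear mixed model with effect for individuals will be used to examine differences in (log) dendritic cell density between groups", with comparisons "between groups and between corneal and conjunctival locations". It adds: "Pairwise comparisons between groups and locations will be obtained within the model". For multiplicity: "P-values for multiple comparisons between locations will be adjusted by Holm's step-down Bonferroni method". It does not mention visit or time, a residual covariance, or whether the individual effect is only an intercept.

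The data layout is in other sections. Section 14 has confocal images taken "at the baseline visits and at each follow-up visit", with follow-up at "24 hours, 7 days and 14 days during the treatment period, and post-treatment at days 21 and 28". That makes six imaging visits, and Table 1 agrees (Visits 2 to 7). Section 10 states: "Images will be captured from the right eye only". The number of locations is not fixed for this trial. Section 5 reports an earlier study that found differences from controls at the "corneal centre, corneal periphery, limbus, and conjunctiva but not at the inferior whorl", which is five sites.

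Section 4 makes change in density the primary endpoint and puts time course and topographical distribution in the aim and the research question.

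**The concern.** A single individual effect with independent residuals makes any two readings from one person equally correlated, whether they share a location, a visit or neither. Suppose a participant's limbus is persistently cell-rich relative to that participant's own cornea. The six limbal readings then carry the same personal deviation six times, but the model averages it down as if it were fresh noise at each visit. The standard error of a location difference comes out too small. Likewise, readings at several locations on one bad allergy day share a deviation that the model does not recognise.

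This is a matter of error structure. Adding visit or baseline as fixed effects does not remove it. Holm does not help either, because the p-values that enter it are already too small. What is at stake is the topographical part of the aim, the arm comparison at a single site (Section 8 bases the sample size on the central cornea), and the arm difference in change between visits.

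**Working it through.** **Inputs from the protocol.** Six imaging visits, V = 6 (Section 14, Table 1). One eye (Section 10). 25 completers per arm, 75 in all (Section 8). Alpha 0.05 (Section 8). The protocol states no error rate for the location contrasts, so there is no figure of its own to reproduce beyond the nominal 5%.

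**Assumptions.** L = 5 locations, borrowed from the earlier study in Section 5. Normal log densities and no missing data. All visits in one model, with a person intercept, independent residuals and full location-by-visit means. The variance components are u (person), a (person-by-location), b (person-by-visit) and e (residual). All are assumed, and ranges are shown.

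**Residual variance that the model estimates.**
M = e + a·V(L−1)/(LV−1) + b·L(V−1)/(LV−1) = e + (24/29)a + (25/29)b.

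**One location pair, averaged over visits.** True variance over model variance is (e + 6a)/M. The rejection rate is 2Φ(−1.96/√ratio). With b = 0 and r = a/e, the ratio is (1 + 6r)/(1 + 0.828r):

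| r | variance ratio | rejection, formula | rejection, simulated |
|---|---|---|---|
| 0 | 1.00 | 5.0% | 4.9% |
| 0.05 | 1.30/1.041 = 1.25 | 7.9% | 8.7% |
| 0.10 | 1.60/1.083 = 1.48 | 10.7% | 11.1% |
| 0.25 | 2.50/1.207 = 2.07 | 17.3% | 17.4% |
| 0.50 | 4.00/1.414 = 2.83 | 24.4% | 23.8% |
| 1 | 7.00/1.828 = 3.83 | 31.7% | 31.4% |

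The simulation used 75 participants and 4,000 runs per row, so its own error is about half a percentage point. With two locations instead of five it gave 5.0%, 9.0%, 11.2%, 18.8%, 26.2% and 36.0%.

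**Holm.** If all five locations were truly equal, the chance of any false location finding after Holm was 4.6%, 8.0%, 14.2%, 29.8%, 45.0% and 61.0% in the same order.

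**Arm contrasts.** Components are written u/a/b/e and total 1.

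- *Overall arm effect, all locations and visits.* Simulated with two arms of 25 and r from 0 to 1: 4.3% to 5.1%. It is unaffected.
- *Arm difference at one location, visits pooled.* The true variance per person is u + a + b/6 + e/6. The model uses u* + M/6, where u* = (30u + 6a + 5b + e − M)/30. At 0.30/0.10/0.10/0.50, M = 0.669, u* = 0.331 and the ratio is 0.500/0.4425 = 1.13: 6.5% by formula, 5.6% simulated. At 0.20/0.30/0.10/0.40, M = 0.7345, u* = 0.2655 and the ratio is 0.583/0.388 = 1.50: 11.0% by formula, 10.1% simulated.
- *Arm difference in change between two visits, averaged over locations.* The ratio is (e + 5b)/M. At 0.30/0.10/0.10/0.50 it is 1.00/0.669 = 1.49: 10.9% by formula, 9.8% simulated. With b = 0 it is e/M, which is below 1. Simulated rejection then falls to 3.1%, 2.0% and 0.7% at r = 0.25, 0.5 and 1, so power is lost.

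**Two checks.** With a person-by-location effect added, the location pair rejected at 4.7% to 5.6% for every r from 0 to 2. With the stated model fitted to one visit at a time, it rejected at 4.5% to 5.7%.

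**The case against.** The strongest reply is that Section 18 is brief rather than wrong. It does not say intercept only, does not say that residuals are independent, and does not say that visits are pooled. Covariance structure and degrees of freedom are often left to a statistical analysis plan, and none is shown here. This stands in part: a reader might infer that the protocol treats six visits as independent replicates, and the text does not say so. Even a bare person intercept correlates visits within a person; what it lacks is the extra correlation at the same location or the same visit. The reply does not dispose of the point, because Section 18 does name a dependence term, and that term is not adequate for repeated location-by-visit data.

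A second reply is that some readings avoid the problem. Fitted one visit at a time, location contrasts hold their level. If the response is change from baseline to one visit, a persistent location profile cancels. Both stand. However, Section 18 describes log density rather than change, and separate models by visit give no contrast between visits, which the time-course aim needs.

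Third, Section 5 reports that density differed between most locations, with no difference between corneal centre and inferior whorl. Most location nulls are therefore implausible, and the after-Holm figures, which assume all five equal, overstate the practical risk. This stands. For real differences the consequence is intervals that are too narrow.

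Finally, a reader might infer that the treatment comparison as a whole is invalid. It is not: the overall arm effect holds its level, and the error in arm-by-change contrasts depends on which variance dominates.

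**Conclusion.** The point holds conditionally. If the Section 18 model is run as written on all six visits, location p-values and intervals can be too small. For one pair, rejection is about 8–9% when person-by-location variance is 5% of the residual, about 11% at 10%, roughly 24% at 50%, and 5% at zero. Under the assumed components, the arm difference at one location runs at about 6% to 10%, and the arm difference in change at about 1% to 10%.

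These sizes rest on assumed variances, five assumed locations, balanced data and pooled visits; the protocol fixes none of the four. It would go too far to say that location tests reject far above 5% as a matter of fact. Section 5 shows that locations differ on average and in how they separate patients from controls, but it does not give the person-by-location variance. The change is worth making because topography and time course are stated aims and the remedy is small. It is not a flaw in the overall arm comparison.

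**What to change.** In Section 18, replace the reference to an individual effect with a statement along these lines: log density from all imaging visits enters one linear mixed model with random effects for participant, participant-by-location and participant-by-visit (or an equivalent participant-level covariance structured by location and visit), with Satterthwaite or Kenward-Roger degrees of freedom. Location, arm-at-location and arm-by-visit contrasts are taken from this model, and Holm is then applied to the location comparisons as planned.

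The cost is one sentence in the protocol and two extra RANDOM lines in SPSS MIXED. No new data are needed. The downside is wider location intervals. Where the added variances prove negligible, the results will be close to those of the simpler model.
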